5.0 Inclusion and Exclusion Criteria/ Study Population

Study Population

Participants in the proposed study will be child/caregiver dyads seeking outpatient burn care at MUSC. Caregivers will be parents or legal guardians of the child participant. We expect that females and minorities will be very well represented in this study based on demographic data collected during our retrospective review of pilot data. We anticipate that 40% of youth recruited into the study will be girls. Caregivers' age may vary but the majority will be 25-45 years. Additionally, women are expected to comprise the majority (85%) of participating caregivers. Because mothers are more often the caregivers of injured patients, it is anticipated that more women will be recruited as caregiver providers than men. Participants of all racial/ethnic backgrounds will be eligible for this study. We estimate that Black or African American children and providers will comprise approximately than 50% of our sample. Given the low prevalence of individuals of Hispanic ethnicity in SC (5%) and data from our pilot study, we estimate that our sample will be comprised of approximately 5% of Hispanic youth in this study.

Inclusion Criteria for child/caregiver dyads

Participants will be eligible for enrollment if:

- (1) the patient (child) is < 18 years of age;
- (2) the patient is diagnosed with a partial thickness burn between <1% TBSA – 20% TBSA by a pediatric burn surgeon;

- (3) the burn is being treated with advanced burn dressing therapy (e.g., SilvadeneTM, PolysporinTM, ActicoatTM, MepilexTM, or MepitelTM) or skin substitutes;
- (4) the burn is evaluated by the MUSC burn team within 72 hours of injury;
- (5) the patient's caregiver (parent or legal guardian) is able to speak, hear, and understand English, as determined during study recruitment procedures;
- (6) the patient/caregiver owns and is capable of using a smart device (an Android or iOS smartphone) with permission to download TOBI app from the Google Store or AppStore;
- (7) able to comply with outpatient clinic visits.

There are no exclusion criteria. All participants who meet inclusion criteria would be eligible to participate in the study.

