7.0 Setting

The proposed study will be conducted at the MUSC campus and remotely via telephone/videoconference and TOBI. Participants will be recruited into the study during their initial visit to the MUSC outpatient burn clinic, hospital floor, or pediatric emergency room for the treatment of pediatric burns. Patients that visit and get discharged from the pediatric emergency room in the after-hours or patients that were missed due to staff unavailability will be contacted by phone by a clinical care team member within 72 hours. Informed consent with caregivers and assent with children, when applicable, will be conducted in a private room at Shawn Jenkins Children's Hospital or virtually at the patient's private location using secure videoconferencing.

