8.0 Recruitment Methods

The MUSC Pediatric Burn program provides the only tertiary burn care in the state to >200 pediatric patients annually. We will use a convenience sampling strategy to recruit 64 patient/caregiver dyads who have undergone a face-to-face (FTF) clinical encounter with an MUSC burn professional at the outpatient burn clinic, the hospital floor, or the pediatric emergency room. Patients will be seen in person and prescribed therapy by our burn experts in our standard practice. Patient/caregiver dyads who meet the inclusion criteria will be considered eligible for enrollment.

Recruitment will be initiated in-person in MUSC's outpatient burn clinic setting, the hospital floor, or pediatric emergency room. Patients/caregivers that visit and get discharged from the pediatric emergency room in the after-hours or patients that were missed due to staff unavailability will be contacted by phone by a member of the clinical care team within 72 hours. Once a possible study candidate dyad is identified, patients will be asked about participating in the feasibility RCT and the study will be explained by study staff, either in-person or by phone/virtually. Study staff will include members of the clinical care team (e.g., burn nurse, physician) and research staff (e.g., clinical trial coordinator). Initial mention of the study will occur with a member of the clinical care team who is also a research team member. If the caregiver expresses interest, study staff will screen potential participants for eligibility and proceed with reviewing informed consent (and assent if applicable) and will address the risks and benefits of the study. For potential participants contacted by phone, the review of informed consent will occur virtually. If potential participants indicate further interest in the study, study staff will obtain written or electronic informed consent from caregivers and assent from children, if applicable. After enrollment, patient/caregiver dyads will be randomized. The randomization scheme will yield at least 32 patients per treatment group.

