The following data will be collected and analyzed: Feasibility processes include recruitment and drop-out proportions, protocol adherence and patient and provider satisfaction will be assessed at 1 month. We will use 95% CIs for proportions to estimate dichotomous outcomes (proportions of subjects who agree to participate out of the number who are initially approached), the proportion who are adherent to protocol (e.g. opening messages, bi-monthly provider reports), the proportion who report satisfaction with intervention, and the proportion who exit the study prematurely (drop out). In addition, frequency distributions will be developed describing reasons for provider and patient protocol non-adherence, drop out and problems encountered such as technology glitches, etc. For the continuous feasibility measures (e.g., number of technology help requests, provider and patient satisfaction scores from patient surveys and end-of-study interview), frequency distributions and the median and mean responses (with 95% confidence intervals) will be obtained. For relevant categorical feasibility measures, chi-square tests will be used to compare the 2 groups. Pooled *t*-test (or Wilcoxon rank sum tests) will be used to compare the groups for continuous feasibility measures. We will also compare demographic and clinical characteristics for those who were eligible for study versus those who were not eligible and for those who adhered to the study protocol (study completers) versus those who did not adhere (non-adherers and drop-outs).

Quantitative analyses: In preparation for a subsequent adequately powered RCT, the planned primary clinical outcomes will be investigated. Those include variables such as time to healing, time to treatment change, and number of clinical encounters. Determination whether a wound has healed or become infected will be made at routine intervals based on clinical judgement from baseline through the day of burn healing and a final assessment 1 month after it was determined as 'healed'. Analyses for these measures

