focus on variability and precision of estimates rather than magnitude of effect sizes. 95% confidence intervals (CIs) of the difference in mean days to healing (or treatment change/infection) between interventions will be obtained. In addition, survival distributions and their 95% CIs will be obtained for each intervention arm using the Kaplan-Meier product limit method. Further, 95% CIs for hazard ratios will be obtained using Cox proportional hazards regression to model time to healing (treatment change) as a function of the intervention. In the future RCT, generalized linear mixed models (GLMM) will be used to obtain estimates of the variances of the clinical outcomes and the covariance structure of longitudinal measures as critical input information for determination of sample size (and hence adequate power) [82, 83]. Frequency distributions of AEs and SAEs will be used to characterize each intervention group. Analyses of caregiver data will include pre- and post-treatment group differences (TOBI vs. FTF) to understand factors related to caregiver well-being and adjustment following mHealth burn treatment and possible predictors of outcomes. These analyses may include mixed design repeated measures analyses of variance (ANOVAs) and regressions.

When the study is concluded, after 6 years all records related to the study will be destroyed. Furthermore, all staff will sign confidentiality agreements, and training sessions will emphasize the critical importance of confidentiality. The likelihood that these methods will effectively protect the confidentiality of participants is considered to be extremely high. Based on our experience with previous research projects, it is believed that these procedures will be effective in protecting confidentiality of subjects and minimizing any potential risk from participation.

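### Day 0 for days to healing is not stated, and the planned models leave out the time from injury to randomisation although the injury date is recorded

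*Combined protocol and SAP*

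**What the plan says.** The combined protocol and SAP treats healing time in the quantitative analyses of section 11.0. Wound status is to be determined at routine intervals "from baseline through the day of burn healing", with a final check one month later. The analyses are a 95% interval for the difference in mean days to healing, Kaplan-Meier curves by arm, and a Cox regression "to model time to healing (treatment change) as a function of the intervention". No covariate is named, and day 0 is not defined. The section says that these analyses are about variability and precision rather than effect size.

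The time from injury to entry is set in three other places. Section 5.0 requires that "the burn is evaluated by the MUSC burn team within 72 hours of injury". Section 7.0 says "Participants will be recruited into the study during their initial visit". It adds that after-hours or missed patients "will be contacted by phone by a clinical care team member within 72 hours"; sections 8.0 and 9.0 repeat this. None of them says when the second 72 hours begins, and none limits the time from phone contact to consent or randomisation. Section 10.0 collects the injury date at chart review and stratifies randomisation by provider only.

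**The concern.** Healing is a process that starts at the injury. A child randomised on day 3 has already completed three days of it, which a child randomised on day 0 has not. If days are counted from randomisation and the model holds only the arm, that head start goes into the residual variance, and a chance difference in lag between arms goes into the estimated effect.

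Without a stated origin, one analyst could count from injury and another from first evaluation, enrolment or randomisation, and they would report different SDs. This matters more than usual here, because section 11.0 presents the variability of these outcomes as preparation for a powered trial. A planner who receives an SD needs to know which clock it belongs to and whether it is adjusted.

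**Working it through.** The plan gives no SD, effect or power for healing time, and section 6.0 calls the sample size pragmatic. There is therefore no figure of the plan's own to reproduce.

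**Inputs.** T is days from injury to healing and L is days from injury to randomisation. There are 32 dyads per arm. SD(T) is assumed to be 4, 5 or 6 days. Section 10.0 has most burns healing in 2-4 weeks; taking that 14-day range as four SDs gives 14/4 = 3.5, so a smaller value is possible. The lag scenarios are:
- (a) every child randomised at the initial visit, L uniform on 0-3 days: Var(L) = 3²/12 = 0.75.
- (b) a quarter recruited by phone (assumed), with a second independent 0-3 day delay: 0.75 + 0.25 × 0.75 + 0.25 × 0.75 × 1.5² = 1.36.
- (c) every child recruited by phone: 0.75 + 0.75 = 1.50.
- (d) extreme case, L uniform on 0-6 days for every child: 6²/12 = 3.00.

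**Step 1: added variance.** If L is independent of T, Var(T − L) = Var(T) + Var(L), so the added share is Var(L)/Var(T).

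| Lag | Var(L) | SD 4 | SD 5 | SD 6 |
|---|---|---|---|---|
| (a) 0-3 days | 0.75 | 4.7% | 3.0% | 2.1% |
| (b) 25% by phone | 1.36 | 8.5% | 5.4% | 3.8% |
| (c) all by phone | 1.50 | 9.4% | 6.0% | 4.2% |
| (d) uniform 0-6 | 3.00 | 18.8% | 12.0% | 8.3% |

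With SD 3.5 (variance 12.25), rows (a), (b) and (d) become 6%, 11% and 24%.

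**Step 2: interval width for the mean difference.** Width is proportional to the SD, so removing the lag narrows it by 1 − √[Var(T)/(Var(T) + Var(L))]. From SD 6 to SD 4 this is 1.0-2.3% in (a), 1.8-4.0% in (b), 2.0-4.4% in (c) and 3.9-8.2% in (d). The covariate costs one degree of freedom. Its chance correlation with arm also raises the variance of the adjusted difference by about 1/(64 − 4) = 1.7%, or 0.8% in width. Net of that, (a) to (c) give roughly 0.2% to 3.6%.

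**Step 3: lag correlated with healing time.** Then Var(T − L) = Var(T) + Var(L) − 2ρ·SD(T)·SD(L). This falls below Var(T) once ρ exceeds SD(L)/(2·SD(T)), so moving the origin to injury could raise the variance. Adjustment behaves differently: with L in the linear model, the residual variance is Var(T)(1 − ρ²), which is never above Var(T − L). For SD(T) 3.5, scenario (d) and ρ = 0.3, Var(T − L) = 12.25 + 3 − 2 × 0.3 × 3.5 × 1.732 = 11.6, against 12.25 × 0.91 = 11.1 after adjustment.

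**Step 4: chance imbalance.** The 95% range of the difference in mean lag between arms is ±1.96 × SD(L) × √(2/32). That is ±0.42 days in (a) and ±0.85 days in (d).

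**Step 5: Cox model.** In a simulation of 32 per arm with lag (d), SD 4, an assumed mean of 18 days, a 1.5-day effect and no censoring, the mean standard error of the log hazard ratio was 0.259 without the lag and 0.264 with it. Adjustment does not tighten that interval.

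**The case against.** The strongest reply is that the plan never says it counts from baseline. The quoted sentence gives the period over which wounds are examined. Since the injury date is collected, counting from injury is equally open, and then the lag adds nothing. That stands: the documents support an undefined origin, not a wrong one.

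Several stronger readings are tempting, and the documents do not support them.
- A reader might apply a 0-6 day lag to everyone. Section 7.0 recruits at the initial visit and keeps the phone for missed or after-hours patients. Even the all-phone scenario has a variance of 1.5, not 3.0.
- A reader might say that this spoils the variance Aim 2 is meant to supply. Aim 2 in section 1.0 names time to treatment of a complication, sleep, adherence and in-person visits. Healing time enters only in section 11.0.
- A reader might say that every interval is widened. Intervals for recruitment, drop-out and satisfaction do not use this clock, and the Cox interval does not narrow.
- A reader might say that the next trial will be too large. If that trial counts from randomisation without adjustment, the unadjusted SD is the right planning value.

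On size, a variance on 62 degrees of freedom has a 95% range of about −28% to +47%. Roughly weekly assessment could add more noise than the lag: 7²/12 = 4.1 days² if the delay in detecting healing is uniform over a week. Both points stand and keep the matter minor. Neither is a reason to leave in a component that recorded data can remove. Randomisation already prevents systematic bias between arms, and the interval already allows for chance imbalance; adjustment only corrects the imbalance that occurs.

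**Conclusion.** The point holds as a modest refinement. Section 11.0 should define day 0, and its comparison by arm alone leaves out a known source of spread that the trial will already have recorded. If the clock starts at randomisation, the added variance is about 2-5% with a 0-3 day lag and 4-8.5% with a quarter recruited by phone. It reaches 8-19% only in the extreme case. Removing it narrows the mean-difference interval by about 1-5% before the small cost of the covariate.

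These sizes rest on assumed healing SDs of 4 to 6 days, assumed lag distributions and independence of lag and healing. A positive correlation would shrink or reverse the gain from moving the origin to injury, but would not make adjustment harmful beyond the cost of the extra term. The 6-day figure is 72 + 72 hours and requires that the phone window start at the visit; later consent could lengthen it. The point concerns the clinical outcomes analysed in section 11.0. It does not touch the validity of the randomised comparison.

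**What to change.** In section 11.0:
- State that days to healing run from randomisation (day 0).
- Add days from injury to randomisation as a covariate in the mean-difference model. Add it to the Cox model too, noting that there it corrects chance imbalance and is not expected to narrow the interval.
- Report three SDs of healing time: from randomisation, from injury, and the residual SD after adjustment. The next trial can then take the one that matches its own analysis.

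The cost is SAP wording, one degree of freedom and the small loss shown above. No new data, visits or participants are needed. At the same time, the outcome lists in Aim 2 and section 11.0 should be reconciled, so that it is clear whether healing time is one of the outcomes whose variability the study is meant to estimate.

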Aim 1: Assess feasibility of the proposed RCT methodology, including recruitment, participation and attrition, treatment fidelity, safety, and problems associated with equipment.

Aim 2: Obtain estimates of variability for the primary outcome measures: time to treatment of wound complication (e.g., infection, pain, non-healing), patient's sleep, therapy adherence, and FTF clinical visits. These variability estimates are needed to calculate sample size for a subsequent larger, adequately powered RCT to compare the effects of the TOBI intervention with FTF alone.

Aim 3: Examine factors related to caregiver attitudes toward telemedicine and access to health care, as well as caregiver stress, self-efficacy, and well-being in relation to treatment outcomes. Because caregivers randomized to TOBI will be the ones delivering burn treatment under the guidance of a provider through the app, they may experience elevated stress levels and anxiety, and their self-efficacy may influence treatment. Assessing these domains will strengthen our understanding of treatment utilization and outcomes as a function of caregivers' psychological factors. We also would like to assess post-injury caregiver adjustment from a more positive perspective (e.g., personal strengths, relating to others in times of need, spiritual change, appreciation of life), a construct that is conspicuously scarce in the scientific literature on caregivers of burn-injured children. Treatment feasibility and satisfaction will also be assessed.

The proposed mHealth intervention may (1) improve the quality of and access to expert burn care for pediatric surgical patients and their families and (2) relieve the burden on burn providers by allowing them to remotely direct treatment in the patient's home. TOBI has significant clinical utility and strong potential to influence access to care and alter the doctor-patient relationship, enabling healthcare providers to prescribe the right intervention at the right dose at the right time for each patient. Findings from this study will demonstrate the feasibility of testing a scalable, low-cost intervention in a multicenter RCT.

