Clinical data will be collected on case report forms by the clinical care team (e.g., burn nurse, physician) and entered into the REDCap database in a coded manner by a research assistant (who is blind to the treatment condition to reduce bias during data entry) at clinically determined intervals per routine care based on clinical judgment with TOBI or FTF (see table below). The duration and number of clinical encounters for both conditions will be guided by best clinical practice and each patient's needs. On average, most burns that meet the study eligibility criteria require 2-5 visits and heal within 2-4 weeks. Case report forms will be generated with study ID only, with no identifiable PHI in order to protect patient's privacy. Data collected at intervals will include adherence to prescribed wound care, change in therapy, wound complications, day of healing, pain scores, sleep problems, unexpected return to clinic or emergency room (see Clinical Case Report Form attached). App metrics, such as number of videoconferences, number of text-messages, number of photos, and scripted messages by burn professional will be recorded by the app software and exported at the end of the study. Images of wounds will not be stored for the purposes of this study. They may be uploaded by clinical care team members into the patient's medical record as part of standard care procedures (outside of the study). Adherence to therapy will be defined as parent/patient performance of prescribed wound care through the end of treatment. Overall compliance with therapy is defined as documentation of healed burn through TOBI or FTF. Clinical data collection will continue until 1 month after the burn is diagnosed as healed by a burn physician in either condition (FTF or TOBI).

At 1-month, caregivers will be asked to complete the post-treatment questionnaires by phone or virtually using the REDCap survey, using a public link and study ID to identify their survey. This assessment will include measures about attitudes toward telemedicine, perception of healthcare access, affect, depression, anxiety, perceived stress, posttraumatic growth, treatment satisfaction, and app feasibility (TOBI only group) (see measures attached). Collected data will be entered into REDCap by the study staff. Overall, participation rate will be recorded. Families will receive \$30 following completion of post-treatment assessment.

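### The planned difference in mean days to treatment change or infection gives event-free children no value, and a mean does not suit an event as rare as infection

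*Combined protocol and SAP*

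**What the plan says.** The quantitative analysis text in Section 11.0 plans a contrast of means for three events: "95% confidence intervals (CIs) of the difference in mean days to healing (or treatment change/infection) between interventions will be obtained". Three further analyses follow:

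- Kaplan-Meier, with no outcome named: "survival distributions and their 95% CIs will be obtained for each intervention arm using the Kaplan-Meier product limit method".
- A hazard ratio from "Cox proportional hazards regression to model time to healing (treatment change) as a function of the intervention". Infection is not named here.
- For safety: "Frequency distributions of AEs and SAEs will be used to characterize each intervention group".

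The purpose is set by Aim 2 in Section 1.0: "Obtain estimates of variability for the primary outcome measures: time to treatment of wound complication (e.g., infection, pain, non-healing". The aim says these estimates will feed the sample size of the next trial. Section 11.0 describes the planned primary clinical outcomes in similar but not identical terms: "Those include variables such as time to healing, time to treatment change, and number of clinical encounters".

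On follow-up, Section 11.0 has healing and infection judged "from baseline through the day of burn healing and a final assessment 1 month after it was determined as" healed. Section 10.0 says "Clinical data collection will continue until 1 month after the burn is diagnosed as healed by a burn physician". No section states what a child without a treatment change or infection contributes to the mean, and none gives a censoring, truncation or competing-event rule for it.

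**The concern.** A child who never has the event has no number of days to it. For healing this hardly matters. For infection it concerns almost everyone: Section 14.0 puts the adult rate near 5%, describes infection in the site's own outpatients as very rare, and reports none among 32 pilot patients treated with TOBI.

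The analyst must therefore choose a rule, and two simple ones suggest themselves. Averaging only children with the event compares subgroups formed after randomisation and leaves out how often the event occurs. Entering event-free children at a last day turns the result largely into a healing contrast, in which the arm that heals sooner seems to reach infection sooner. Section 3.0 reports a pilot signal of earlier detection of healing with TOBI, so this artefact could count against the intervention.

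At stake are the variability estimates that Aim 2 is meant to deliver. An interval that cannot be computed would be noticed. A last-day rule would not, because it fills the table.

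**Working it through.** The plan gives no SD, event count or power to reproduce, because Section 6.0 sets the sample size on pragmatic grounds.

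**Inputs**
- 32 per arm (Section 10.0).
- Infection risk p: 5% (adult figure, Section 14.0); 2% and 1% are assumed for children.
- Treatment change, or treatment change and infection as one composite: no rate is given, so 10%, 20% and 30% are assumed.
- Healing: most burns by 14 days (Section 2.0). Assumed: lognormal with log-SD 0.35, median 14 days in one arm and 11, 13 or 14 in the other.
- Assumed: constant event hazard that stops at healing, set so that both arms have the same cumulative risk unless stated otherwise.
- Last observed day: healing + about 30 days (Section 10.0).

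**Step 1. Events only: can the interval be formed?**
P(at least one arm empty) = 1 − [1 − (1−p)^32]². A pooled interval also fails with exactly one event in each arm, which adds [32p(1−p)^31]².

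At 5%: 0.95^32 = 0.194, and 1 − 0.806² = 0.350. Then 32 × 0.05 × 0.95^31 = 0.326, whose square is 0.106. The total is 0.456.

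| Risk | At least one arm empty | No pooled interval |
|---|---|---|
| 1% | 0.92 | 0.98 |
| 2% | 0.77 | 0.89 |
| 5% | 0.35 | 0.46 |
| 10% | 0.07 | 0.08 |
| 20% | 0.002 | 0.002 |
| 30% | <0.001 | <0.001 |

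Infection analysed alone will often have no interval. Treatment change, or the composite, usually will.

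**Step 2. Events only: what does it measure?**
With median healing of 14 days, simulation gives a mean of 7.90 days at 20% risk and 8.17 days at 10%. Halving the risk moves the summary by 0.3 day. With 20% risk in both arms and healing at 14 vs 11 days, the means are 7.9 and 6.2. That is a 1.7-day gap with no difference in risk. At 32 × 0.20 = 6.4 events per arm and SDs of 5.7 and 4.5, the standard error is √[(5.7² + 4.5²)/6.4] ≈ 2.9, so the half-width is a little over 6 days.

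**Step 3. Event-free children entered at a last day (5% risk in both arms)**
With medians of 14 vs 11 days, mean healing is 14.9 vs 11.7, a gap of 3.2 days. Entering the healing day gives 14.5 vs 11.4, a gap of 3.1 days. Entering healing + 30 adds 0.95 × 30 = 28.5 days to both arms, so the gap is unchanged. The precision does change:

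| Median healing | Gap | Interval excludes zero: healing day | Interval excludes zero: healing + 30 |
|---|---|---|---|
| 14 vs 11 | 3.1 days | 70% | 31% |
| 14 vs 13 | 1.0 day | 12% | 8% |
| equal | 0 | 5% | 5% |

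If the hazard rather than the cumulative risk is equal, the 14 vs 11 gap at healing + 30 is about 2.7 days.

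**Step 4. The SD as an input to the next trial**
At 5% risk and median healing of 14 days, the SD is 5.5 days with the healing day and 9.6 with healing + 30. In variances, 9.6² − 5.5² = 92.2 − 30.3 = 61.9, and 61.9/92.2 = 0.67. Adding 30 days to every child would leave the variance unchanged. About two-thirds of it therefore arises because event-free children gain 30 days and children with the event do not. That SD mostly records whether the event occurred.

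**The case against.** The other side has a good case.

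- The sentences after the mean contrast plan Kaplan-Meier without excluding any outcome, and a Cox hazard ratio that names treatment change. For treatment change, a randomised contrast that handles censoring is therefore already planned. This stands, and it narrows the gap mainly to infection. For infection, frequencies per group are planned as part of the adverse event tables, but no between-arm difference with an interval. Kaplan-Meier curves could also yield a restricted mean, but the plan does not say so.
- The last-day figures need an assumed healing difference and a rule that the plan never adopts. This stands: with equal healing the artefact vanishes. Section 11.0 also plans a judgement on infection one month after healing, so events after healing, which the simulation leaves out, are possible.
- If Aim 2 means the delay from complication to treatment, that quantity exists only in children with a complication, and averaging over them is the natural summary. This stands as description. It does not make the average a randomised comparison.
- These outcomes are secondary and no hypothesis is tested. This also stands, and it limits the severity.

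A reader might go further and infer that a last-observed-day rule would usually give an interval excluding zero. The documents do not support that. The 70% belongs to entering the healing day. Section 10.0 puts the last observed day about a month later, where the figure is 31%, and 8% for a one-day healing difference. Nor do they support the inference that treatment change has no usable analysis, or that its mean could not be computed.

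**Conclusion.** The point holds and is minor. The plan names a mean for events that most children will not have, and gives those children no value. For infection analysed alone, the events-only interval fails with probability 0.46 at the adult rate and 0.89 to 0.98 at the assumed 2% and 1%. For treatment change or a composite it is usually computable (failure 0.08 at an assumed 10%, 0.002 at 20%), but it compares a post-randomisation subgroup and barely responds to risk. A last-day rule gives a gap that follows healing. At healing + 30 it also gives an SD that is a poor variability input for Aim 2.

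The binomial results rest only on 32 per arm and the stated risks. The last-day results also rest on the assumed healing distribution, the assumed healing difference and no events after healing. The healing mean and the Kaplan-Meier and Cox plans are not in question.

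**What to change.** Limit the difference in mean days to healing, and add text along these lines:

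> For treatment change and for infection, each reported separately and in all randomised children, we will give the number and proportion with the event per arm (exact 95% CI), the risk difference with a 95% CI suited to small counts (for example Newcombe), and the cumulative incidence by a stated day. Cumulative incidence will come from the Kaplan-Meier analysis, or from Aalen-Johansen with healing as a competing event if follow-up for the event ends at healing.

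The Kaplan-Meier sentence should name the outcomes it covers. If time to treatment of a complication means the delay from complication to treatment, report it descriptively among children with a complication and label it as not a randomised comparison.

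These summaries always return a result. With no events in 32, the exact upper limit is 1 − 0.025^(1/32) = 10.9%. Newcombe risk differences are −10.7 to +10.7 points for 0/32 vs 0/32, −20.1 to +5.4 for 0/32 vs 2/32, and −27.0 to +8.4 for 3/32 vs 6/32. The choice of interval method is optional. What matters is that frequency is compared between the arms with an interval.

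The cost is a few sentences and no new data. A reporting day and the end of follow-up for each event must be stated. Children lost early count as event-free in the simple proportion, so it should be read beside the cumulative incidence, which censors them.
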